The primary objective of this study is to determine the infusion rate of Ang II that is necessary to return systolic blood pressure (SBP) to within 5% of baseline or greater in patients with essential hypertension taking ACE inhibitors, ARBs, or different classes of antihypertensive agents for greater than two months and further to determine the plasma levels of different RAAS components (as measured by the Attoquant system) in patients preoperatively, following induction, at a steady state infusion level of Ang II, and 30 minutes after surgical incision. In addition, a secondary objective is to determine how the levels of various RAAS components in the blood compare based on the method of analysis (liquid chromatography versus radioimmunoassay).

Methods and Measures

Design

Patients scheduled for general surgery who are evaluated in our preoperative assessment clinic (PAC) will be recruited for participation. Recruitment and consent for participation in the study will be performed prior to day of surgery via telephone screen or in person at the PAC. If patient is consented via telephone screen and agrees to participate, a consent form will be electronically mailed, or physically mailed to the patient. Patient will be asked to sign consent and return electronically or by physical mail. Patient will also sign consent in person on day of, prior to surgery. Once initial consent is received, (Giapreza) will be prepared and ready for use during surgery. Women of childbearing age will be asked about level of sexual activity and use of birth control. Given that the safety of Ang II has not been demonstrated in pregnant patients, the only women of childbearing age who will be considered for recruitment are those that (1) are not sexually active; or (2) are sexually active and use an acceptable method of birth control; or (3) are surgically sterile; or (4) are at least 2 years postmenopausal; or (5) have a monogamous partner who is surgically sterile; or (6) are practicing double barrier contraception. Once recruited, we will verify on the day of surgery that the patient is still agreeable to participate in the study.

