Women of childbearing age will be asked to undergo a pregnancy test on the day of surgery and provide a negative result. The determination of whether the patient takes their anti-hypertensive on the day of surgery will be determined by the PAC's normal practice and will be unaltered by this study. Our goal would be to enroll and obtain data on 15 patients for each group: (Arm 1) ACE group, (Arm 2) ARB group, and (Arm 3) patients on any other class of antihypertensive agent for greater than two months. There will also be a fourth comparison group (Arm 4) consisting of up to the first 15 enrolled patients whose SBP does not drop below the 80% baseline threshold after intubation. It would be our intent to continue enrolling patients until a sample size of 15 patients for each of the 3 groups (Arms 1,2,3) have completed the protocol and received the trial medication. Once each of the three experimental arms of the study (Arms 1,2,3) have 15 patients, enrollment in the fourth comparison group (Arm 4) will cease regardless of whether or not it has met the 15 patient goal. Based on an estimated incidence of hypotension of 40-60% following induction of anesthesia, we expect to have to consent approximately 90 patients. This is to account for patients who do not meet study criteria, thereby reaching our goal of 45 experimental patients and the tentative 15 patient comparison group.¹

There will be a total of 5 blood samples taken at three time points throughout the duration of the study. Patients will have an IV line placed in the holding area prior to surgery. At this time, we will draw the first two 10cc blood samples (one for LC/MS analysis, one for RIA analysis) for study purposes while the patient is in the preoperative holding room. The RIA labs will be processed at Wake Forest Baptist Medical Center and is sponsored by a grant from the NHLBI of the NIH. , and the LC/MS labs will be analyzed through an external contracted laboratory to gain information for RAAS component testing. An initial set of vital signs including heart rate (HR),

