non-invasive blood pressure (BP), and oxygen saturation (SpO₂) will be checked in the holding room. We will also record all medications taken on the day of surgery. Once in the operating room and following placement of vital sign monitors, another non-invasive BP will be checked prior to anesthetic induction. This reading will be used as the baseline systolic blood pressure (SBP). Sequential Compression Devices (SCD) will be used for venous thromboembolism (VTE) prophylaxis during surgery and these will be applied prior to induction of general anesthesia. General anesthesia will then be induced with 1.5 mg/kg of propofol followed by 0.8 mg/kg rocuronium and the patient will be intubated. If the dose of propofol is inadequate to achieve loss of consciousness, additional propofol may be given at the discretion of the attending anesthesiologist. In addition, a rapid sequence induction and intubation may also be allowed if clinically indicated for the safety of the patient as determined by the attending anesthesiologist. Anesthesia will be maintained with isoflurane in fresh gas such as oxygen and/or air. No vasopressors will be administered at induction or during intubation unless the SBP is less than 80% of baseline for greater than 4 consecutive minutes. In that case, a rescue vasopressor such as phenylephrine will be given.

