Following intubation and before initial surgical incision, the BP will be checked using a non-invasive BP cuff every minute for 10 minutes. If a SBP that is less than 80% of the baseline reading is detected, the clinical team will immediately cycle the BP cuff in order to confirm the presence of hypotension. At this point an infusion of Ang II will be initiated at 2 ng/kg/min through a peripheral IV (although the recommended starting dose of Ang II is listed as 20ng/kg/min, this dosing regimen is based on patients in shock. The package insert also states that doses as low as 1.25ng/kg/min may be effective). Starting at a low dose will be important since patients taking ACE inhibitors may be more sensitive to Ang II. The BP will be checked every minute. The half-life of angiotensin 2 is < 1 minute and time to peak pharmacologic affect is less than 30-35 seconds so it will be necessary to monitor the blood pressure once per minute. The infusion will be increased at the discretion of the clinical team based on the response of the patient until a SBP within 5% of the baseline SBP has been achieved (although the rate will not be increased by more than 15ng/kg/min at a time and the rate will not exceed 80ng/kg/min based on the package insert dosing instructions). If the patient remains hypotensive despite use of the maximum dose of angiotensin II, then angiotensin II will be discontinued, the patient will be excluded from the study, and the blood pressure will be treated using conventional vasopressors. If a patient experiences SBP < 80% baseline for greater than four consecutive minutes after initiating Ang II, then a rescue vasopressor such as phenylephrine will be administered. This will be important for patients taking ARBs as they may be less sensitive to Ang II.

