Arm 3: Patients on any other antihypertensive medication, and must not be on an ACEi or ARB.

Arm 4: Patients who qualify for arm 1, 2, or 3 but whose SBP does not drop below 80% of baseline in the first 10 minutes after intubation.

- **Inclusion Criteria**

- Diagnosis of hypertension and treatment for greater than 2 months and on the following medications
 - ACE inhibitors, in addition they can also be on other classes of antihypertensive medication except for ARB
 - ARBs, in addition they can also be on other classes of antihypertensive medication except for ACEi
 - Any other antihypertensive medication, and must not be on an ACEi or ARB
- Patients undergoing general anesthesia
- American Society of Anesthesiologists physical status 1-3
- Age ≥ 40 given that hypertension is not prevalent below this age

- **Exclusion Criteria**

- American Society of Anesthesiologists physical status 4-6
- BMI > 40
- History of deep venous thrombosis / thromboembolic disease
- History of stroke,
- Baseline SBP of ≥ 160 mmHg,
- History of myocardial infarction or cardiac stents
- Difficult airway
- Asthma
- Diagnosis of congestive heart failure of any stage, regardless of preserved or reduced ejection fraction; this includes both systolic heart failure and diastolic heart failure;
- Diagnosis of chronic obstructive pulmonary disease of any stage; this includes diagnoses of chronic bronchitis and emphysema
- Pregnant patients (safety of Ang II in pregnancy is unknown)

- Patients at increased risk for venous thromboembolic events such as current diagnosis of cancer and/or diagnosis of blood clotting disorders
- **Sample Size**
Our goal would be to enroll and obtain data on 15 patients for each group: ACE group, ARB group, and patients on any other class of antihypertensive agent for greater than 2 months. In addition, we would like to obtain data for up to 15 patients in the comparison group (Arm 4). The sample size was chosen due to its similarity to the ATHOS II dose-finding trial.⁹ It would be our intent to continue enrolling patients until a sample size of 15 patients for all 3 experimental groups has been reached. Based on an estimated incidence of hypotension of 40-60%, we expect to have to consent approximately 90 patients.¹ This is not a multisite study.

Interventions and Interactions

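### Is a forecast of about 90 consents too low for an assumed hypotension incidence of 40-60%?

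*Combined protocol and SAP*

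**What the plan says.** The Design section under Methods and Measures asks for 15 patients in each of the ACE inhibitor, ARB and other-antihypertensive arms. Recruitment goes on until the patients in each arm "have completed the protocol and received the trial medication". The forecast is: "Based on an estimated incidence of hypotension of 40-60% following induction of anesthesia, we expect to have to consent approximately 90 patients". The plan adds that this number allows for patients who fail the study criteria, "thereby reaching our goal of 45 experimental patients and the tentative 15 patient comparison group". The Sample Size section repeats the forecast: "we expect to have to consent approximately 90 patients".

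Arm 4 takes up to 15 patients whose pressure does not fall below the threshold. It closes when the three treated arms are full, whether or not it has reached 15.

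Several steps can remove a patient after consent:

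- The Design section says that "we will verify on the day of surgery that the patient is still agreeable to participate in the study", and it requires a negative pregnancy test on the day of surgery for women of childbearing age.
- The Exclusion Criteria list "Baseline SBP of ≥ 160 mmHg", and the Design section takes baseline from the reading made in the operating room before induction.
- For a patient still hypotensive at the maximum rate, the Design section says that "the patient will be excluded from the study".

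No rate is given for any of these. The Design section also limits radioimmunoassay (RIA) analysis to at most 90 patients.

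**The concern.** The plan quotes a range of incidence but gives a single forecast, and that forecast fits only the middle of the range if nobody is lost for another reason. At 50%, the 45 consents beyond the target are all used up by patients who never become hypotensive. Nothing then remains for withdrawal, a high operating-room baseline or exclusion at the maximum rate. Patients lost in these ways must be replaced, because only completed and treated patients count.

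If 90 were a fixed enrolment, the trial would probably miss its target at the lower incidence, and the comparison of mean doses between arms would rest on fewer than 15 per arm. The reuse of 90 for the RIA samples raises a second worry: if more than 90 patients enter, the plan does not say whose samples are analysed.

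**Working it through.** **Inputs.** Target: 3 × 15 = 45 (Design). Incidence p: 40% to 60% (Design and Sample Size). Forecast: about 90 (both sections). The documents give no loss rate and no single planning incidence.

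**Reproducing the plan's figure.** Expected consents = 45 / p:

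- p = 0.40: 45 / 0.40 = 112.5, so 113
- p = 0.50: 45 / 0.50 = 90
- p = 0.60: 45 / 0.60 = 75

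The midpoint with no other loss gives 90 exactly. Other readings also reach it:

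- 60% incidence with 16.7% loss: 45 / (0.60 × 0.833) = 90
- 55% incidence with 9.1% loss: 45 / (0.55 × 0.909) = 90
- One arm each at 40%, 50% and 60%: 15/0.40 + 15/0.50 + 15/0.60 = 37.5 + 30 + 25 = 92.5

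The plan does not say which of these it used, so 50% with zero loss is an inference.

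**What 90 consents yield.** The expected number hypotensive is 90p. The chance of at least 45 is the upper tail of a binomial with 90 trials, assuming independent patients, equal incidence in the arms and new consents only for arms still open.

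| Incidence | Expected hypotensive | Chance of at least 45 |
|---|---|---|
| 40% | 36 | 3.5% |
| 50% | 45 | 54.2% |
| 60% | 54 | 97.9% |

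A chance near one half at 50% is what a forecast set at the expected value must give.

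**Adding loss.** With a loss fraction L after consent, need = 45 / (p(1 − L)). For an assumed L of 5% to 20%:

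- p = 0.40: 118.4 to 140.6, so 119 to 141
- p = 0.50: 94.7 to 112.5, so 95 to 113
- p = 0.60: 78.9 to 93.75, so 79 to 94

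The loss that 90 can absorb is 1 − 45/(90p): none at 40% (9 patients short), 0% at 50% and 16.7% at 60%.

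**Arm 4.** The non-hypotensive patients among 90 number 54, 45 and 36 at 40%, 50% and 60%. Even 75 consents at 60% leave 75 × 0.40 = 30. Arm 4's 15 places do not drive the number of consents.

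**Limits of the 75 to 113 range.** It holds only if a full arm stops taking consents, which the plan does not state. If all arms stayed open with an equal mix of patients, simulation puts the expected consents at about 137, 110 and 92 for 40%, 50% and 60%.

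**What depends on 90.** The stopping rule counts completed, treated patients per arm. The Analytical Plan compares mean doses between those arms and does not use the number consented. The RIA limit counts patients whose samples are analysed. The first RIA sample is drawn in the holding area on the day of surgery, so people who drop out before then need not supply one.

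**The case for a change.** The best argument for a change is that it costs little and the weakness is real. A forecast drawn from a 40-60% range should carry a range of its own. At 40% no loss rate makes 90 sufficient, and at 50% any loss takes the expected need above 90. The study drug is made ready after initial consent, so preparation grows with consents. Comparing the two assay methods is a stated secondary objective, and the plan does not say which patients would be left out of RIA beyond 90.

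The arithmetic in this stands, and so does the missing RIA rule. The consequence is small. The plan calls 90 an approximate expectation, and at 50% with 5% loss the need is 95, which that wording covers. It also says the number is meant to allow for patients who fail the criteria, so an assumption of no loss cannot be attributed to it. Patients give an initial consent and sign again on the day, and the plan does not say which of these the 90 counts. If it is the second, withdrawal at the day-of-surgery check comes before the count.

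Raising the RIA number to match consents would confuse two different counts and call for more grant-supported assays. If more than 90 patients were sampled, taking them in order of enrolment up to the limit is the obvious reading.

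**Conclusion.** No change is needed. About 90 consents is a correct midpoint forecast: it equals 45 / 0.50, within an expected need of roughly 75 to 113 before other losses. It is optimistic if incidence is near 40% or if losses after consent are appreciable, and a reader planning recruitment should bear that in mind. The shortfall would be in the forecast alone. Enrolment continues to 15 completed patients per arm, so the target of 45 and the comparison of doses do not depend on 90.

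Restating the number as a range would bring no gain in what the trial does or can conclude, and the range would itself rest on an arm-closing rule and a loss rate that the plan does not give. Which patients to assay if more than 90 are sampled, and when to stop consenting for a full arm, are gaps that study staff can fill sensibly.

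This conclusion rests on 90 being a forecast and not a cap, which the plan's enrolment rule supports. The binomial figures assume independent patients and the same incidence in each arm; the 5% to 20% loss is an assumption used only to show scale.

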Appendix 1: Data Collection Form

Study ID: _____

**A dose finding trial for angiotensin II (Giapreza) in hypertensive adults on
angiotensin converting enzyme inhibitors and angiotensin receptor blockers
with anesthesia-mediated hypotension**

DATA COLLECTION SHEET

A dose finding trial for angiotensin II (Giapreza) in hypertensive adults on angiotensin converting enzyme inhibitors and angiotensin receptor blockers with anesthesia-mediated hypotension

Study ID: _____ Age: _____ ASA PS: _____

Gender: M / F UPT: + / - / NA

Surgery date: _____ Surgical procedure: _____

Attending Anesthesiologist: _____

Antihypertensive group: ACE / ARB / other

Antihypertensive medication: _____ Duration of therapy: _____

Preoperative creatinine: _____ Diabetes: No / NIDDM / IDDM

Peripheral vascular disease: Y / N

DVT prophylaxis: SCD / SQ heparin / SQ enoxaparin / other _____

STUDY ID: _____

A dose finding trial for angiotensin II (Glipreza) in hypertensive adults on angiotensin converting enzyme inhibitors and angiotensin receptor blockers with anesthesia-mediated hypotension

1) Holding room data (Time: _____)

Vital signs	HR	
	NIBP/MAP	
	SpO ₂	

Medications taken DOS

LC/MS RAAS sample in holding
 WFBH labs—blood AND urine
 Urine NOT collected (reason): _____

2) OR pre-induction/Baseline (Time: _____)

NIBP/MAP	
----------	--

Induction

Time: _____

(1.5 mg/kg propofol, 0.8 mg/kg rocuronium; avoid pressors)

3) OR post-intubation

Time post-intubation	NIBP/MAP	Confirmatory BP (If <80% baseline)
1 min		
2 min		
3 min		
4 min		
5 min		
6 min		
7 min		
8 min		
9 min		
10 min		

IF ATII infusion started, see next page

IV fluid total PRIOR to ATII administration: _____

Time angiotensin II infusion started: _____

Goal BP +/- 5% of baseline, time reached: _____

ATII infusion at goal BP for 5 minutes, then:

VS/data	HR	
	NIBP/MAP	
	SpO ₂	
	ET Isoflurane (%)	
	Final angiotensin II rate (ng/kg/min)	

LC/MS RAAS sample

LC/MS RAAS sample 30 minutes post-incision

Time infusion stopped: _____

IVF total AFTER ATII administration complete: _____

If no hypotension (< 80% baseline) encountered:

Move to group IV (first 15 patients only)
 LC/MS RAAS draw 10 minutes post-intubation
 LC/MS RAAS sample 30 minutes post-incision
 >>OR<<
 Exclude patient from LC/MS analysis
 Discard first LC/MS sample from holding area

STUDY ID: _____

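### Baseline SBP is one unrepeated cuff reading that sets both the 80% trigger and the titration target, which tilts the treated arms slightly toward chance-high baselines and Arm 4 toward chance-low ones

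*Combined protocol and SAP*

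**What the plan says.** In the Combined protocol and SAP (Methods and Measures, Design), once the patient is in the operating room with monitors on, "another non-invasive BP will be checked prior to anesthetic induction", and then: "This reading will be used as the baseline systolic blood pressure (SBP"). The data collection form in Appendix 1 has one NIBP/MAP cell under "2) OR pre-induction/Baseline (Time". A blood pressure is also taken earlier ("non-invasive blood pressure (BP), and oxygen saturation (SpO₂) will be checked in the holding room"), but it plays no part in the baseline.

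That single number then serves several purposes:

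- **Trigger.** "If a SBP that is less than 80% of the baseline reading is detected, the clinical team will immediately cycle the BP cuff". Only the low reading is repeated.
- **Allocation.** Arm 4 is made up of up to the first 15 "patients whose SBP does not drop below the 80% baseline threshold after intubation".
- **Target.** Angiotensin II is titrated until SBP is within 5% of baseline or higher, and the Analytical Plan makes the mean dose needed to get there the primary outcome.
- **Exclusion.** The criteria list "Baseline SBP of ≥ 160 mmHg". They do not say when this is measured; the link to the operating-room reading is through the defined term.

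**The concern.** A cuff reading is the patient's usual pressure plus error. Selecting patients because a later pressure is below 80% of one such reading favours those whose reading was high by chance, which is ordinary regression to the mean. The same error then raises the level to which they are titrated. Patients whose reading was low by chance tend to go to Arm 4.

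The plan already treats one cuff reading as too uncertain to start treatment on, since it asks for a repeat of the low value. Repeating that value cannot correct an error in the baseline with which it is compared.

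Two results are exposed: the absolute mean dose reported for each treated arm, and the description of RAAS levels in treated patients beside Arm 4.

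**Working it through.** **1. The plan's own figure.** The one derived number that depends on the trigger is the consent target of approximately 90 (Sample Size). Treated patients needed: 3 x 15 = 45. At the midpoint of the stated 40-60% incidence, 45 / 0.50 = 90, which matches. At 40% it is 45 / 0.40 = 112.5, so 113; at 60% it is 45 / 0.60 = 75. Repeating the baseline leaves the 45 and the midpoint figure of 90 essentially unchanged.

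**2. Assumed inputs.** The documents give no SDs for blood pressure, so all of these are assumptions:

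- usual SBP: mean 136, SD 12 mmHg
- post-induction SBP as a fraction of usual: mean 0.785, SD 0.09
- post-induction cuff error: SD 5 mmHg
- single baseline reading error: SD s = 4, 6 or 8 mmHg

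**3. Model.** Baseline = usual SBP + error. A patient is excluded if baseline is 160 or more, and treated if a reading and its repeat are both below 0.80 x baseline. Required rise = 0.95 x baseline - true post-induction SBP. For the mean of three independent readings the error SD is s/√3, a fall of 1 - 1/√3 = 42%. Incidence in the model is about 47%, inside the plan's range.

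**4. Results (mmHg; one reading → mean of three).**

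| s | Mean baseline error, treated arms | Mean baseline error, Arm 4 | SD of required rise, treated |
|---|---|---|---|
| 4 | +0.7 → +0.3 | -0.8 → -0.3 | 8.6 → 8.4 |
| 6 | +1.5 → +0.6 | -1.8 → -0.6 | 8.9 → 8.5 |
| 8 | +2.4 → +0.9 | -3.0 → -1.1 | 9.2 → 8.7 |

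The target moves by 0.95 times the baseline error: 0.95 x 0.7 = 0.7 and 0.95 x 2.4 = 2.3 mmHg. Against a mean required rise of about 33 mmHg, that is 0.7/33 = 2% to 2.3/33 = 7%. The SD of the required rise falls by only 2 to 6% (before rounding).

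**5. Ten post-intubation checks.** The plan checks pressure every minute for 10 minutes. With ten chances to trigger, a mean fraction of 0.82 (to keep incidence at about 51-52%), constant true post-induction SBP and independent cuff errors, the treated-arm error stays within the range above, the Arm 4 error reaches about -3.3 mmHg at s = 8, and the required rise is about 27 mmHg.

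**6. The 160 mmHg exclusion.** It removes some chance-high readings. In the step 3 model with s = 6, moving mean SBP from 136 to 150 cuts the treated-arm error from +1.5 to +0.5 mmHg.

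**7. A second model.** With mean SBP 138 (SD 14), s = 8, SD of the fall 12 percentage points and 50% triggering, the probability of being treated is 0.62 after a chance-high baseline and 0.39 after a chance-low one. Mean error is +1.5 mmHg in treated patients (+2.3 without the exclusion) and -2.9 in Arm 4. Across 108 scenarios (mean SBP 130-150, s = 5-12, SD of the fall 8-16 points, 40-60% triggering), the treated-minus-Arm 4 difference is always positive, from 1.3 to 12.1 mmHg. The treated-arm error alone runs from -1.5 to +6.3, and is near zero or negative only when mean SBP is assumed to be 145-150.

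**8. Correlated readings.** With correlation r, the error variance of a mean of three is s² x (1 + 2r)/3. At r = 0.5 this is two-thirds of s², so the SD falls by 1 - √(2/3) = 18%. The selection bias is roughly proportional to the error variance, so about one-third of it is removed, against about two-thirds with independent readings.

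**The case against.** The plan states one operational baseline and applies it consistently, and a shift of 1 to 2 mmHg is small beside a target that is open above and a rate raised at the clinical team's discretion. That stands, and it limits the point to minor severity. Several stronger readings are tempting, and the documents do not support them:

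- **That the comparison between ACE, ARB and other arms is biased.** Arms 1-3 share the same baseline rule. If cuff error is similar across arms, the shift is common and largely cancels in the t-tests.
- **That the required dose becomes much noisier.** The patient-level SD of error in the target does fall from 3.7, 5.4 or 6.9 to 2.2, 3.2 or 4.2 mmHg with three readings. But real differences between patients dominate the required rise, and selection uses the same baseline, so its total spread barely changes.
- **That the 160 mmHg limit adds to the inflation.** It works in the opposite direction.
- **That repeating the baseline would prevent many patients without a true 20% fall from being treated.** With a single trigger check their share goes from 6-10% to about 4.5-6.5%. With ten checks it goes only from 23-27% to 22-24%, because the repeated post-induction checks cause most of the misclassification.
- **That a planned test against Arm 4 is compromised.** The Analytical Plan lists mean RAAS values in four populations and specifies no such test.

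What remains is the direction of the selection between treated patients and Arm 4, which held in every scenario.

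**Conclusion.** The point holds as a modest selection effect. With error SD 4-8 mmHg, mean SBP 136 mmHg and independent errors, treated-arm baselines are about 0.7-2.4 mmHg too high and Arm 4 baselines about 0.8-3.3 mmHg too low, beside a required rise of about 27-33 mmHg. The difference between treated patients and Arm 4 is robust in sign. The treated-arm inflation is not: it shrinks or vanishes if mean SBP lies close to the 160 mmHg limit. All sizes rest on assumed variances.

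A reader might infer a stated error in the mean dose. The documents give no dose-to-pressure relation with which to convert mmHg into ng/kg/min, so only the likely direction for the absolute mean dose (upward) can be given.

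**What to change.** In the Design section, take three consecutive cuff readings before induction, after monitors are placed, and define baseline SBP as their mean wherever the term is used, including the exclusion criterion. Give the Appendix 1 form three boxes and a mean in place of one cell. Leave all percentage thresholds and clinical rules as they are.

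Costs and limits:

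- About two minutes more before induction, with no extra staff or equipment. The readings follow monitor placement, so this time is not absorbed by it.
- The mmHg equivalents of every baseline-based limit shift slightly in individual patients, so the clinical investigators should agree the new definition.
- The gain is smaller if consecutive readings are correlated (error SD down about 18% at correlation 0.5, against 42% if independent).
- A sustained rise from anxiety before induction is not removed by averaging readings taken together.
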